Document Version No.:	V5.0	Document Date:	13-JUN-2022

Pharmacokinetic (PK) Set: all subjects who received active study medication, had no major protocol deviations impacting PK evaluation and with available PK data.

In general, analyses of efficacy will be conducted using the FAS, PP and FU sets, analyses of safety will be conducted using the Safety Set and FU SAF, and analyses of PK will be conducted using the PK Set.

The actual treatment will be derived as follows, based on daily e-diary IMP intake data:

Subjects received a different kit of active linzagolix or placebo for each month, and a different kit for addback or placebo for each 3-month period.

The number of days with one pink tablet, one grey tablet and one red capsule taken based on e-diary IMP intake data for each treatment will be computed. Data from "Today" will be used primarily. If data from today is missing, data from "Yesterday" of the following day will be considered. If the e-diary is not completed for a day (neither "Today" nor "Yesterday" of following day), it will be assumed that no intake of drug was taken on that day.

Further rules are as follows:

- Treatment administration errors:
 - If a subject received placebo with placebo ABT in more than 50% of days, then the actual treatment group will be placebo with placebo ABT.
 - Otherwise, the active treatment group (combined with add-back or placebo add-back) with the most days taken will be assigned.
 - If the number of days is equal for two treatments groups containing active treatment then LGX 200 mg with ABT will be assigned.
- If a subject discontinued, only data received up to discontinuation will be used.
- It is possible that the derived actual treatment group does not correspond to any of the planned treatment groups. In that case actual treatment group will be assigned to the planned treatment group with same dose of active treatment. Example: LGX 75mg with ABT will be assigned to LGX 75mg with placebo ABT; LGX 200mg with placebo ABT will be assigned to LGX 200mg with ABT. A listing with such cases will be provided.

3.2. **Protocol Violations**

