7.5. Appendix E: Mapping rules for ediary data

Table 8 Mapping Rules for

Device

Cas e #	impacte d visit	Patient status	Schedul e of daily diary	impact on data	Cytel action on IMP intake data	Cytel action on Menstrual data	Cytel mapping	cut off date (from eCRF)
1	Month 6	patient was included in EXT	remain ed in MAIN TREAT MENT (due to Covid remote visit or to site error in diary comple tion)	data present in the Main datasets should be considere d for the analysis of the extension study	mapping	n/a	from MAIN TREAT to EXT TREAT	First IMP intake in EXT

Sponsor:	ObsEva			
Protocol:	18-OBE2109-003			
Document Version No.:	V5.0	Document Date:	13-JUN-2022	

2	Month 6	patient was included in EXT	resched uled to MAIN FU (due to site error in diary comple tion)	data present in the Main datasets should be considere d for the analysis of the extension study	n/a - missing in final DB	n/a	from MAIN FU to EXT TREAT	First IMP intake in EXT
3	Month 6	patient entered MAIN FU	resched uled to EXT TREAT MENT (site error in diary comple tion)	data present in the Extension datasets should be considere d for the analysis of the Main study	"Is the subject eligible to the 6 months treatment free follow-up?" is YES> delete answers to YIMPI and IMPI	n/a	from EXT TREAT to MAIN FU	MONTH 6 visit date

 Sponsor:
 ObsEva

 Protocol:
 18-OBE2109-003

Document Version No.:	V5.0	Document Date:	13-JUN-2022

4	Month 6	patient entered MAIN FU	remain ed in MAIN TREAT MENT (due to Covid remote visit or to site error in diary comple tion)	Data regarding IMP intake will be present for this period	"Is the subject eligible to the 6 months treatment free follow-up?" is YES> delete answers to YIMPI and IMPI	n/a	n/a - remain in MAIN DB	MONTH 6 visit date
5	Month 6	whatever status: DUPLICATE ENTRIES	patient entered diary data in both Main and Extensi on studies each day	duplicate s data will be present across the datasets	CASE by CASE review	- cleaning nee	ded	

Sponsor:	ObsEva			
Protocol:	18-OBE2109-003			
Document Version No.:	V5.0	Document Date:	13-JUN-2022	

6	Day 1	patient entered MAIN TREATMENT	remain ed in SCREEN ING (due to site error in diary comple tion)	Data regarding IMP intake will not be present for this period and data regarding menstrua I periods will be present	n/a - missing in final DB	delete the answers to "is it your Menstrual period?" and start date questions, if any	n/a - remain in MAIN DB	First IMP intake in MAIN

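### SAP 3.1 lets missing eDiary days, rather than documented exposure, place a woman in the 200 mg + ABT group for the safety analyses

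*SAP*

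**What the plan says.** SAP 3.1 opens the derivation in general terms: "The actual treatment will be derived as follows, based on daily e-diary IMP intake data". The quantity counted is "The number of days with one pink tablet, one grey tablet and one red capsule taken based on e-diary IMP intake data", separately for each treatment. If the *Today* answer is missing, the *Yesterday* answer from the next day's entry is used. If both are missing, "it will be assumed that no intake of drug was taken on that day".

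Three assignment rules follow under the label "Treatment administration errors":

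- Placebo: "If a subject received placebo with placebo ABT in more than 50% of days", the woman is placebo.
- Otherwise she goes to the active group with the most days. There is no minimum.
- Tie: "If the number of days is equal for two treatments groups containing active treatment then LGX 200 mg with ABT will be assigned".

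For women who stopped early, only data up to discontinuation count. The Safety Set and Follow-up Safety Set are analysed by this derived treatment. The FAS and Per Protocol Set use randomised treatment.

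SAP Appendix E, Table 8, case 6 describes devices left on the screening schedule after Day 1: "Data regarding IMP intake will not be present for this period". The intake data are then simply missing from the final database.

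**The concern.** The placebo and active conditions are not symmetric. Placebo must exceed a fixed share of days, whereas an active group needs only more days than the other active group. The SAP gives no outcome for a woman who has no active days and does not pass the placebo threshold. A program that follows the text compares zero days on 75 mg with zero days on 200 mg, finds a tie, and assigns 200 mg + ABT.

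Adverse events including hot flush, BMD, ECG, laboratory data, biopsies and time to first menses are all tabulated by this variable. Among women who took only their own kits, gaps can move a woman into 200 mg + ABT but never out of it. Placebo women placed there would dilute the safety profile of the arm in which the effect of add-back therapy on bone loss is a central question.

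**Working it through.** **Inputs.** Dosing runs from Day 1 to the day before Month 6 (Day 169), which is 168 days (Protocol 11.2 and 10.2). The rule is as described above. The minimum diary completeness for efficacy is 12 of 28 days (SAP 4.6.2.1.2); 12/28 = 42.9%, which agrees with the SAP's 43%.

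**Step 1: own kits only, calendar days as denominator.** The placebo condition is d/168 > 0.5, where d is the number of covered days, so d must be at least 85 (85/168 = 50.6%).

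| Covered days | Placebo woman | 75 mg woman | 200 mg + ABT woman |
|---|---|---|---|
| 85 or more | placebo | 75 mg | 200 mg + ABT |
| 84 | 200 mg + ABT | 75 mg | 200 mg + ABT |
| 1 | 200 mg + ABT | 75 mg | 200 mg + ABT |
| 0 | 200 mg + ABT | 200 mg + ABT | 200 mg + ABT |

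The last row can occur within the Safety Set. The first dose is taken at the site and timed in the eCRF (Protocol 10.2.2.1), so a woman can qualify as dosed with no diary intake at all.

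**Step 2: recorded-intake days as denominator.** A placebo-only woman with one recorded day has 1/1 = 100% and stays placebo. Only the zero row still fails, and it fails in every arm.

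**Step 3: effect of back-filling.** Each entry supplies its own day and, if needed, the day before. Patterns are repeated over 168 days.

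| Diary pattern | Entries | Covered days | Result for a placebo woman (calendar days) |
|---|---|---|---|
| 3 alternate days per week | 72 | 144 (86%) | placebo |
| 3 consecutive days per week | 72 | 96 (57%) | placebo |
| one run of 14 per 28 days | 84 | 90 (54%) | placebo |
| one run of 13 per 28 days | 78 | 84 (50%) | 200 mg + ABT |
| one run of 12 per 28 days | 72 | 78 (46%) | 200 mg + ABT |
| 2 consecutive days per week | 48 | 72 (43%) | 200 mg + ABT |

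With the same 72 entries, a woman can land on either side. Clustering of the gaps decides it.

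**Step 4: a documented wrong kit.** Suppose a placebo woman received one 28-day active 75 mg kit by mistake.

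- Complete diary: 140/168 = 83%, so placebo.
- Diary covering 55% of days: 77 placebo days and 15 days on 75 mg; 77/168 = 46%, so 75 mg.
- Same diary over recorded-intake days: 77/(77 + 15) = 84%, so placebo, matching the complete diary.

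Over calendar days she needs more than 84 of her 140 placebo days recorded (60%). With two wrong kits it is more than 84 of 112 (75%). Her exposure is unchanged; only the diary differs.

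**Step 5: scale, as an illustration.** The documents give no count. Assume k = 2 to 15 placebo women are added to an arm of 150. The Phase 2b figures for 200 mg without ABT are hot flush 42.1% against 10.9% on placebo at week 12, and spine BMD −2.602% at week 24 (Protocol 5.5.3 and 5.6). Placebo BMD change is assumed to be 0.

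- Hot flush: (150 × 42.1 + k × 10.9)/(150 + k) = 41.7% (k = 2) to 39.3% (k = 15).
- BMD: −2.602 × 150/(150 + k) = −2.57% to −2.37%.

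**The case against.** **Scope.** The three rules stand under a heading about administration errors. A woman given only placebo kits has had no such error, and calling zero against zero a tie between active groups is strained. This is a fair reading. But the opening sentence covers every subject and no other rule is supplied for women without an error, so a programmer has only this text to implement.

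**Denominator.** The SAP says days, not all days, and over recorded-intake days the problem nearly disappears (Step 2). Against that, an unfilled day never enters the numerator. Declaring it a day without intake therefore changes the proportion only if it stays in the denominator. SAP 4.8.1.2 uses the same fallback for compliance and there divides by the days in the period. Calendar days is the more natural reading, though it is not stated.

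**Conservatism.** Keeping women exposed to active drug out of the placebo group is a legitimate safety convention. That justifies the asymmetry where active intake is documented. It does not justify reaching an active group through absent records.

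**Likelihood of gaps.** Alarms, site alerts and remote compliance checks (Protocol 10.3.2) and the 75% screening requirement work against long gaps. Table 8, case 6 gives neither duration nor count, and for the other device Table 9 recovers intake data by mapping. One lost 28-day month would still leave 140 of 168 days. These points stand and limit the likely number of women.

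A reader might infer that any placebo woman with a sparse diary is reclassified, or that every woman who just meets the 12-of-28 efficacy minimum is. The documents do not support either inference. The minimum counts entries within each 28-day window, the treatment rule counts days after back-filling, and 72 entries can cover from 78 to 144 days.

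**Conclusion.** The rule is wrong as written, because missing diary data can determine a woman's safety arm. On the calendar-day reading, a placebo-only woman with 84 or fewer of 168 covered days is analysed as 200 mg + ABT, which requires long, clustered gaps. On either denominator, a woman of any arm with no recorded intake is analysed the same way. Where a wrong active kit was given, missing days still count against placebo on the calendar-day reading.

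This rests on two readings the SAP leaves open: that the rules apply to all subjects, and that the share is taken over calendar days. The SAP permits the misclassification but does not unambiguously require it.

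The number of women is unknown and probably small. A reader might take Step 5 as evidence that harm in the 200 mg + ABT arm will be materially understated. It is not: the 2 to 15 women are assumed, and the figures come from 200 mg alone, whereas ABT is added to limit bone loss. Step 5 shows direction and rough scale only. The co-primary and ranked secondary analyses on the FAS and Per Protocol Set are untouched.

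**What to change.** Amend SAP 3.1 as follows:

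1. Actual treatment equals randomised treatment unless IWRS or drug accountability documents a wrong kit.
2. For documented errors, take the proportion over days with recorded intake, or over days covered by each dispensed kit, and state that denominator.
3. No subject is assigned to an active group for which she has neither documented dispensing nor recorded intake. This removes the zero-against-zero tie.

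A conservative rule that places women with documented active exposure in the active arm may be kept, provided it is written as such. A listing of every woman whose actual and randomised treatment differ would make the outcome visible; the listing now planned covers only derived combinations that match no planned group.

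The cost is a short SAP amendment and a few lines of code. The IWRS and accountability data already exist, and SAP 4.8.1.2 already takes accountability first and the diary second when computing compliance.

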4. STATISTICAL METHODS

4.1. Sample Size Justification

The planned sample size for this study is 150 subjects per treatment group (450 subjects in total).

An overall two-sided type I error of 0.05 will be used. As there are two linzagolix versus placebo comparisons, Bonferroni corrected p-values will be produced (raw p-values will be multiplied by two prior to comparing to 0.05). The planned sample size considers the hierarchical, fixed sequence testing of the ranked secondary endpoints as well as the co-primary endpoints. The assumptions used for the sample size calculations are based on analyses of clinically meaningful reduction in pain with a stable or decreased use of analgesics from the Phase 2b Edelweiss study. Calculations were performed using East[®] 6.5 software.

One hundred and fifty (150) subjects per treatment group will provide a power greater than 95% to reject the null hypothesis for both co-primary endpoints for either treatment group, assuming a placebo response rate of 14.6% and an active treatment response rate of 48.6% (75 mg, Edelweiss Phase II study results) or 64.7% (200 mg, Edelweiss Phase II study result) for DYS, and a placebo response rate of 18.8% and an active treatment response rate of 42.1% (75 mg, Edelweiss Phase II study result; the response rate for 200 mg in Edelweiss was lower but was inconsistent with the other doses and other timepoints for the same dose and so was not used) for NMPP. In addition, 150 subjects per treatment group provides 85% power to reject the null hypotheses for all the ranked secondary endpoints based on the observed results from the placebo and 200 mg treatment group in the Edelweiss study.

The values used for the sample size calculations assume that these responses rates are what would be seen on average when under treatment including taking into account any subjects who might withdraw from treatment early; therefore the calculations do not need to be further adjusted for dropouts.

4.2. General Statistical Methods and Data Handling

4.2.1. General Methods

All output will be incorporated into Microsoft Excel or Word files, sorted and labeled according to the International Conference on Harmonisation (ICH) recommendations, and formatted to the appropriate page size(s).

Tabulations will be produced for appropriate demographic, baseline, efficacy, pharmacokinetic and safety parameters.

For continuous data and for ordered categorical data, if appropriate, the number of non-missing observations, mean, standard deviation, median, first and third quartiles, minimum and maximum will be calculated, including for change from baseline when applicable. The baseline mean will be calculated

Sponsor:	ObsEva		
Protocol:	18-OBE2109-003		
Document Version No.:	V5.0		

for all subjects based on the FAS. For efficacy endpoints and BMD, a baseline mean will also be calculated for each visit using the baseline data for the subset of subjects who attended that visit, such that the same subjects contribute to the mean for the visit and the mean for the corresponding baseline values. Summary statistics will be based primarily on non-missing values. For ordered categorical data and nominal data, absolute counts and relative frequencies (in %) will be calculated.

This study will be conducted at approximately 100 study sites, resulting in only a few subjects per site on average. Subjects from all sites will be pooled and no adjustment for sites will be carried out in the statistical analyses.

Raw and derived data will be listed.

All statistical hypothesis tests and confidence intervals will be two sided.

4.2.2. Computing Environment

All descriptive statistical analyses will be performed using SAS statistical software (Version 9.4), unless otherwise noted. Medical History and adverse events will be coded using MedDRA available version. Concomitant medications will be coded using World Health Organization (WHO) Drug Dictionary available version.

4.2.3. Methods of Pooling Data

Not applicable to the present study.

4.2.4. Adjustments for Covariates

Adjustments for possible covariates will be described in the appropriate statistical analyses' sections.

4.2.5. Multiple Comparisons/Multiplicity

All statistical hypothesis tests and confidence intervals will be two-sided. To maintain an overall type I error rate of 0.05, as there are two linzagolix versus placebo comparisons, Bonferroni corrected p-values will be produced (raw p-values will be multiplied by two prior to comparing to 0.05), along with corresponding 97.5% confidence intervals.

The two co-primary efficacy endpoints will be clinically meaningful reduction from baseline over the last 28 days of randomized treatment up to the Month 3 visit (i.e., the 4-week period preceding the Month 3 visit) in the mean daily assessment of DYS and of NMPP measured on a VRS, along with a stable or decreased use of analgesics for EAP.

The primary objective will be assessed by testing the following two-sided hypotheses for each co-primary endpoint, for each linzagolix group versus placebo separately:

Null hypothesis (H0): There is no difference in the odds of subjects meeting the primary endpoint for the active treatment group compared to placebo, that is, the odds ratio (OR) equals 1.

Sponsor:	ObsEva		
Protocol:	18-OBE2109-003		
Document Version No.:	V5.0		

H0: OR =1

Alternative hypothesis (H1): There is a difference in the odds of subjects meeting the primary endpoint for the active treatment group compared to placebo, that is, the OR is not equal to 1.

H1: OR ≠ 1

Where odds are equal to the proportion of subjects meeting the endpoint divided by proportion of subjects not meeting the endpoint.

Each linzagolix group will need to demonstrate a statistically significant difference for both co-primary endpoints for the group to be considered more efficacious than placebo, thus maintaining an overall type I error rate of 0.05.

For each linzagolix group that is statistically significantly more efficacious than placebo for the co-primary endpoints, a fixed-sequence testing strategy shall be used within the group to test the ranked secondary endpoints as ordered in Section 2.5.1.2, to maintain the family-wise type I error rate. That is, the comparison for each linzagolix group versus placebo for each ranked endpoint will only be declared statistically significant different if the raw p-value multiplied by two is less than or equal to 0.05 for that endpoint and for all preceding endpoints for that dose versus placebo.

Response rates for DYS and NMPP at each visit will be analyzed to evaluate the changes in pain over time, with nominal Bonferroni corrected p-values used in the comparisons of treatment groups at each visit. These are supportive analyses and will primarily be considered as descriptive. The analyses do not form part of the fixed-sequence strategy being used for the ranked secondary endpoints and will not be fully controlled for an overall type I error rate. However, to maintain consistency with the primary and secondary analyses, Bonferroni corrections will be used due to there being two linzagolix versus placebo comparisons for each endpoint / time point.

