13 DATA ANALYSIS AND STATISTICS

13.1 TEST OF HYPOTHESES

All statistical hypothesis tests and confidence intervals will be two sided. To maintain an overall type I error rate of 0.05, as there are two linzagolix versus placebo comparisons, Bonferoni corrected p-values will be produced (raw p-values will be multiplied by two prior to comparing to 0.05), along with corresponding 97.5% confidence intervals.

The two co-primary efficacy endpoints will be clinically meaningful reduction (see section 13.5.2) over the last 28 days of randomized treatment up to the Month 3 visit (the 4-week period preceding Month 3 visit) from baseline in the mean daily assessment of DYS and of NMPP measured on a VRS, along with a stable or decreased use of analgesics for EAP.

The primary objective will be assessed by testing the following two-sided hypotheses for each co-primary endpoint, for each linzagolix group versus placebo separately:

Null hypothesis (H0): There is no difference in the odds of subjects meeting the primary endpoint for the active treatment group compared to placebo, that is, the odds ratio (OR) equals 1.

$$H_0: OR = 1$$

Alternative hypothesis (H1): There is a difference in the odds of subjects meeting the primary endpoint for the active treatment group compared to placebo, that is, the OR is not equal to 1.

$$H_1: OR \neq 1$$

Where odds are equal to the proportion of subjects meeting the endpoint divided by proportion of subjects not meeting the endpoint.

Each linzagolix group will need to demonstrate a statistically significant difference for both co-primary endpoints in order for the group to be considered more efficacious than placebo, thus maintaining an overall type I error rate of 0.05.

For each linzagolix group that is statistically significantly more efficacious than placebo for the co-primary endpoints, a fixed-sequence testing strategy shall be used within the group to test the ranked secondary endpoints as ordered in Section 7.1.2.1, so as to maintain the family-wise type I error rate. That is, the comparison for each linzagolix group versus placebo for each ranked endpoint will only be declared statistically significant different if the raw p-value multiplied by two is less than or equal to 0.05 for that endpoint and for all preceding endpoints for that dose versus placebo.

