13.6.2 End-of-Treatment Period Analysis

After all subjects have completed the Treatment Period (Month 6), a complete analysis will be performed. This analysis will include all data up to the Month 6 visit. A database lock will be performed prior to unblinding of treatment, and any discrepant data will be clarified before the lock. Since this end-of-treatment-period analysis is the only and final analysis of the primary and ranked secondary endpoints, no additional adjustment of alpha-level is necessary beyond that described in section 13.1. The results for the Treatment Period will be summarized and described in an integrated Clinical Study Report.

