2.5.1.2. Ranked Secondary efficacy endpoints

Ranked secondary efficacy endpoints (in the order of the endpoints to be tested) are:

- Change from baseline to Month 6 in DYS (VRS)
- Change from baseline to Month 6 in NMPP (VRS)
- Change from baseline to Month 6 in dyschezia (Numeric Rating Scale NRS)
- Change from baseline to Month 6 in overall pelvic pain (NRS)
- Change from baseline to Month 6 in the interference of pain with the ability to perform daily activities, measured using the pain dimension of the Endometriosis Health Profile-30 (EHP-30)
- Change from baseline to Month 6 in dyspareunia (VRS)
- No analgesics use for EAP during the preceding 4-week period at Month 6
- No opiate use for EAP during the preceding 4-week period at Month 6

Additional details on ranked secondary endpoints and analyses are provided in Section 4.6.

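### The Bonferroni split between doses is valid but not fully efficient: a dose that rejects its whole chain does not pass its 0.025 to the other dose

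*SAP*

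**What the plan says.** SAP 4.1 sets the overall level: "An overall two-sided type I error of 0.05 will be used". SAP 4.2.5 divides it between the two dose-versus-placebo comparisons ("raw p-values will be multiplied by two prior to comparing to 0.05") and pairs the tests with 97.5% intervals.

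Within a dose the order is fixed. First, "Each linzagolix group will need to demonstrate a statistically significant difference for both co-primary endpoints". Then come the ranked endpoints: "a fixed-sequence testing strategy shall be used within the group to test the ranked secondary endpoints as ordered in Section 2.5.1.2" in the SAP, and "a fixed-sequence testing strategy shall be used within the group to test the ranked secondary endpoints as ordered in Section 7.1.2.1" in protocol 13.1. A ranked result counts only if the "raw p-value multiplied by two is less than or equal to 0.05 for that endpoint and for all preceding endpoints for that dose". That condition looks at the dose's own earlier endpoints and never at the other dose's results.

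There are eight ranked endpoints (SAP 2.5.1.2, protocol 7.1.2.1). The last is "No opiate use for EAP during the preceding 4-week period at Month 6". Protocol 13.6.2 adds no other rule: "no additional adjustment of alpha-level is necessary beyond that described in section 13.1".

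**The concern.** Each dose is a chain: the co-primary pair, then eight ordered endpoints, all at two-sided 0.025. If one dose rejects its whole chain, nothing remains on which its 0.025 could produce an error, yet the plan does not hand that alpha on. The other dose still has to meet raw p ≤ 0.025 (|z| ≥ 2.241), although raw p ≤ 0.05 (|z| ≥ 1.960) would keep the trial within the stated 0.05. At stake is power for the second dose, chiefly on its ranked endpoints. SAP 4.1 states power for all ranked endpoints from placebo and 200 mg data only and gives no such figure for 75 mg.

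**Working it through.** **1. The plan's own power figure.** Inputs from SAP 4.1: n = 150 per group; DYS 14.6% on placebo, 48.6% on 75 mg, 64.7% on 200 mg; NMPP 18.8% on placebo, 42.1% on either dose. With p̄ the mean of the two rates,

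power = Φ{ [ |p₂ − p₁|√n − z(α/2)·√(2p̄(1 − p̄)) ] / √(p₁(1 − p₁) + p₂(1 − p₂)) }.

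NMPP at 0.025: p̄ = 0.3045; (0.233 × 12.247 − 2.241 × 0.6508) / 0.6296 = 2.216; power 98.7%. DYS exceeds 99.99% for both doses. Power for both co-primaries is therefore about 98.7% for either dose, which agrees with the stated figure of more than 95%. The 85% for the ranked endpoints cannot be reproduced, because no effect sizes or standard deviations are given for them.

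**2. Error control with release.** Let a dose that rejects its whole chain pass 0.025 to the other dose.
- True nulls in both chains: neither chain can finish without a false rejection, so the first false rejection is made at 0.025. Over two chains the error is at most 0.025 + 0.025 = 0.05.
- True nulls in one chain only: its first true null is tested at no more than 0.05.
- For the co-primary pair, both must be significant, so the pair's error cannot exceed the level used.

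No current rejection is lost, because no threshold ever falls below 0.025.

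A simulation checked this (300,000 runs per scenario, correlation 0.5 between doses, 0 to 0.9 between endpoints). The maximum error was 0.0493 for the fixed split and 0.0506 with release. The latter is within Monte Carlo error of 0.05, the standard error being √(0.05 × 0.95 / 300,000) = 0.0004. With one dose fully effective and one co-primary null for the other, the error was about 0.025 under the fixed split and 0.050 with release.

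**3. Gain once alpha is released.** Power at 0.05 = Φ(z of power at 0.025 + 2.241 − 1.960).

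| Second-dose hypothesis | At 0.025 | At 0.05 |
|---|---|---|
| NMPP at planning rates (18.8% vs 42.1%) | 98.7% | 99.4% |
| NMPP if active response were 34% (assumed) | 77.5% | 85.1% |
| Ranked endpoint, 70% assumed | 70% | 79.0% |
| Ranked endpoint, 80% assumed | 80% | 86.9% |
| Ranked endpoint, 90% assumed | 90% | 94.1% |

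**4. How often release could happen.** The chain ends with no opiate use. SAP 4.6.4.7, 4.6.4.8 and 4.6.4.10 reduce the opioid-amount and opioid-day analyses to listings because few subjects use opioids, and opioids are not allowed in Ukraine (SAP 4.6.3.6). No rates are given, so these are assumptions, put through the formula in step 1 with n = 150 and α = 0.025:

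| No opiate use, placebo vs active | Power |
|---|---|
| 95% vs 98% | 20% |
| 90% vs 95% | 27% |
| 85% vs 92% | 37% |
| 80% vs 90% | 57% |
| 85% vs 95% | 74% |

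Under each assumption the figure is an upper bound on the chance of completing the chain, since every earlier endpoint must also succeed.

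**5. Average gain.** With release probability r, and ignoring the correlation from the shared placebo arm, an 80% endpoint averages 0.80 + 0.069r. That is 85.9% at r = 0.85, 85.1% at r = 0.74 and 81.9% at r = 0.27.

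**6. Whole-chain illustration.** Assume that 200 mg completes its chain with probability 0.85, that effects are equal across its ranked endpoints, and that endpoint correlation is 0.3 to 0.6. The chance that 75 mg completes its chain then rises from 0.85 to about 0.90 if its effects match 200 mg. It rises from 0.29–0.44 to 0.41–0.55 if each ranked endpoint has 78% power at 0.025.

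**The case against.** A fixed Bonferroni split with a fixed sequence per dose is a recognised, valid choice. It is stated consistently in both documents and matches each test with a 97.5% interval. A sponsor may prefer that simplicity, and a reader who infers that the plan inflates or misstates the type I error would be mistaken. This stands in full.

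Release also has a price. Its ceiling is the same 0.05, but the actual error rises toward it when one dose is fully effective (about 0.025 to about 0.05). The two 97.5% intervals have joint coverage of at least 95%; with one replaced by an ordinary 95% interval, the Bonferroni bound on joint non-coverage becomes 0.025 + 0.05 = 0.075. So it would be wrong to say that the change gives nothing up. It gives up no rejection.

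Two inferences about size also fail. One is that the second dose loses material power on its co-primaries; at the documents' own rates the loss is under 1 point. The other is that release can be expected 85% of the time. That figure is a planning value for 200 mg against placebo, nothing comparable exists for 75 mg, and it sits badly with the SAP's remarks on opioid use.

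None of this removes the point. Alpha does go unused after a complete chain, and using it stays within the error rate the plan already claims.

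**Conclusion.** The multiplicity rule is valid but not fully efficient. An end-of-chain release would keep family-wise error at or below 0.05 and every rejection the present rule makes. This is an optional improvement, not a correction of an error.

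The benefit falls mainly on the second dose's ranked endpoints: 80% becomes 86.9% after release, the 80% being an assumption. On the co-primaries it is negligible unless NMPP response falls well short of plan. How often release would occur is uncertain, and the last endpoint may make it uncommon; the power range for that endpoint rests on assumed rates.

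A reader might conclude that this trial's results should now be re-read at 0.05 for one dose. The documents do not support that. SAP V4.0 already added thresholds derived at the Month 6 database lock. SAP 4.3 has a restricted team unblinded at that lock, with results going to the sponsor once the SAP is updated. V5.0 (13 June 2022) is later still, so a looser rule added to it could not be presented as prespecified.

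**What to change.** Where the blind is still intact, add to the multiplicity section of both protocol and SAP: *If both co-primary endpoints and all ranked endpoints are rejected for one dose, its alpha of 0.025 is passed to the other dose, which is then tested in the same order at two-sided 0.05 (raw p-values).* Do not apply it retrospectively.

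Keep 97.5% intervals as the default display. For a dose tested at 0.05, add a 95% interval (1.960/2.241 = 0.874 of the width) and state that the joint 95% coverage of the two 97.5% intervals then no longer applies.

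The cost is one sentence in each document, raw p-values and a 95% interval in the outputs for the released dose, and the higher actual error described above. No subjects are added and no endpoint is reordered.
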